**11.7 Description of Investigational Agents**

TAK-228 will be supplied as capsules for oral administration. The study drug is available in 3 dose strengths, 1 mg, 3 mg, and 5 mg, each containing 1 mg, 3 mg, and 5 mg of TAK-228, respectively, in

addition to the following inactive ingredients: microcrystalline cellulose (solid filler/diluents), magnesium stearate (lubricant), and hard gelatin capsule. All 3 dose strengths are formulated into size 2 capsules, and each dose strength is differentiated by color, as listed below:

- TAK-228 capsules, 1 mg - white opaque color
- TAK-228 capsules, 3 mg – orange opaque color
- TAK-228 capsules, 5 mg – grey opaque color

Tamoxifen citrate USP is a non-steroidal antiestrogen commercially available in tablet formulation for oral administration. Each tablet contains 10 or 20 mg tamoxifen (equivalent to 15.2 or 30.4 mg tamoxifen citrate, respectively). Tamoxifen is available in generic formulations that may contain the following inactive ingredients depending on the specific generic formulation: croscarmellose sodium, hypromellose, lactose (monohydrate), magnesium stearate, polyethylene glycol 400, povidone, corn starch, and titanium dioxide.

### **11.8 Preparation, Reconstitution, and Dispensation**

TAK-228 study drug will be provided in labeled bottles in accordance with all applicable regulations. Materials provided by the sponsor should be dispensed to patients with clear administration instructions from the investigator. TAK-228 is an anticancer drug and, as with other potentially toxic compounds, caution should be exercised when handling TAK-228 capsules. Tamoxifen is commercially available and will be provided through the patient's pharmacy in accordance with all applicable laws and regulations regarding dispensing of a prescription medication.

### **11.9 Packaging and Labeling**

TAK-228 will be provided by Millennium and will be handled at the investigative site as open label material. Sites must store TAK-228 according to the labeled conditions.

TAK-228 capsules are packaged in 60-cc high-density polyethylene bottles with polypropylene, child-resistant caps and induction seal. For all dose strengths, each bottle contains 30 capsules.

Tamoxifen will be provided through the patient's pharmacy and labeled according to both state and federal laws and regulations.

### **11.10 Storage, Handling, and Accountability**

Upon receipt at the investigative site, the drug should be stored in the original bottles until use and stored at a room temperature of 15°C to 30°C (59°F to 86°F). All temperature excursions will be reported for assessment and authorization for continued use. All investigational supplies will be stored in the original packaging in a secure area with controlled access. All drug supplies should be used before the retest expiry date. Because TAK-228 is an investigational agent, it should be handled with due care. In case of contact with broken capsules, raising dust should be avoided during the cleanup operation. The product may be harmful if inhaled, ingested, or absorbed through the skin. Gloves and protective clothing should be worn during the cleanup operation. The area should be ventilated and the spill site washed after material pickup is complete. The spilled material should be disposed of as hazardous medical waste in compliance with federal, state, and local regulations. In case of contact with the powder (e.g., from a broken capsule), the skin should be washed immediately with soap and copious amounts of water for at least 15 minutes. In case of contact with the eyes, copious amounts of water should be used to flush the eyes for at least 15 minutes. Medical personnel should be notified. Patients will receive instructions for home storage and administration of TAK-228. Accountability for TAK-228 at all study sites is the responsibility of the sponsor-investigator. Tamoxifen should be stored at a controlled room temperature of 20°C to 25°C (68°F to 77°F).

### 11.11 Study Compliance

Study drug will be administered or dispensed only to eligible patients under the supervision of the investigator or identified sub-investigator(s). The appropriate study personnel will maintain records of study drug receipt and dispensing.

### 11.12 Termination of Treatment and/or Study Participation

Patients will be informed that they have the right to withdraw from the study at any time for any reason without prejudice to their medical care. The investigator also has the right to withdraw patients from the study for any of the following reasons:

- AE
- Protocol violation
- Lost to follow-up
- Progressive disease
- Study termination
- Other

At the time of withdrawal, all study procedures outlined for the End of Study visit should be completed. The primary reason for the patient's withdrawal from the study should be recorded in the source documents and CRF.

## 12. CRITERIA FOR RESPONSE

This study is designed to determine the change in Ki67 and pCR rate after TAK-228 in combination with tamoxifen in patients with ER-positive, HER2-negative breast cancer.

### 12.1 Response Evaluation Criteria in Solid Tumors (RECIST) 1.1

The clinical tumor response will be assessed at baseline and before surgery using RECIST 1.1. RECIST 1.1 offers a simplified, conservative, extraction of imaging data for wide application in clinical trials. They presume that linear measures are an adequate substitute for 2-dimensional methods and register four response categories.

#### Target Lesions (Main Tumor)

- Complete Response (CR): Disappearance of all target lesions. Any pathological lymph nodes (whether target or non-target) must have reduction in short axis to < 10 mm.
- Partial Response (PR): At least a 30% decrease in the sum of the diameters of target lesions, using the baseline sum diameters as the reference.
- Progressive Disease (PD): At least a 20% increase in the sum of the diameters of target lesions using the smallest sum while on study (includes the baseline sum) as the reference. In addition to the relative 20% increase, the sum must also demonstrate an absolute increase of at least 5 mm. (Note: the appearance of one or more new lesions is also considered progression)
- Stable Disease (SD): Neither sufficient shrinkage to qualify for PR nor sufficient increase to qualify for PD, using the smallest sum diameters while on study as the reference.

#### Non-Target Lesions (Lymph Nodes)

CR: Disappearance of all non-target lesions and normalization of tumor marker levels. All lymph nodes must be non-pathological in size (< 10 mm short axis). (Note: If tumor markers are initially above the upper normal limit, they must normalize for a patient to be considered in complete clinical response.)

- Non-CR/Non-PD: Persistence of one or more non-target lesion(s) and/or maintenance of tumor marker levels above the normal limits.

- **PD:** Appearance of one or more new lesions and/or *unequivocal progression* of existing non-target lesions. *Unequivocal progression* should not normally trump target lesion status. It must be representative of overall disease status change, not a single lesion increase.

Although a clear progression of “non-target” lesions only is exceptional, the opinion of the treating physician should prevail in such circumstances, and the progression status should be confirmed at a later time by the principal investigator.

## 13. STATISTICAL AND QUANTITATIVE ANALYSES

### 13.1 Statistical Methods

Based on prior data for Ki67 changes in the tamoxifen only arm of the IMPACT trial, we will assume null and alternative hypotheses of 60% and 80% reduction in Ki67, respectively. Transformations of the geometric mean and 95% CI were employed to obtain mean and standard deviation estimates.

As a measure of safety, toxicity will be monitored during the trial based on a beta-binomial model, assuming a priori that the probability of toxicity  $p$  is distributed beta(0.2, 0.8). Study accrual will be suspended and the safety profile of the TAK-228 and tamoxifen combination will be reviewed by the safety monitoring committee if  $P_r(p > .20 | \text{data}) > 0.85$ . This stopping rule yields the following stopping bounds where the numerator represents the number of events needed to suspend accrual and the denominator represents the number treated at that point in the study: 3/6, 4/8, 5/12, 6/16, 7/20, 8/24. An event is defined as progression within 16 weeks. Scenario 1 of the operating characteristics table (see below) indicates that the probability of stopping the study early for progression is very low when progression is uncommon; that is, the study has only a 4.2% chance of stopping early when the true progression rate is only 10%. The study has a 94.3% chance of stopping if the true progression rate is 40% and on average would take only 7 patients to arrive at that conclusion. The stopping rule assumes monitoring begins after 6 patients have been enrolled on study.

Scenario	True $P_r(\text{toxicity})$	$P_r(\text{stop early})$	Median # Pts (25%, 75%)
1	0.10	0.042	28 (28, 28)
2	0.20	0.317	28 (15, 28)
3	0.30	0.723	14 (6, 28)
4	0.40	0.943	7 (6, 13)
5	0.50	0.995	6 (6, 7)

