## 9.3 Duration of Study

Patients will receive TAK-228 QW and tamoxifen QD for 16 weeks. Screening for inclusion in the study will be done within 28 days prior to the day 1 dose of TAK-228 and tamoxifen. Baseline vital signs, labs, physical exam, and biopsy and tumor tissue collection will be done within 7 days prior to the day 1 dose of TAK-228 and tamoxifen. Visits will occur at weeks 1, 3, 4, 6, 8, 12, and 16 and at end of treatment (7 to 10 days after the final dose of study treatment).

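### The accrual-suspension rule counts patients still inside the 16-week window as event-free, so its published operating characteristics hold only if every outcome is known before the next patient enrols

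*Combined protocol and SAP*

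**What the plan says.** Section 13.1 puts a beta(0.2, 0.8) prior on the event probability p. It suspends accrual for committee review when the posterior probability that p exceeds 0.20 is above 0.85. The resulting bounds are "3/6, 4/8, 5/12, 6/16, 7/20, 8/24", where "the denominator represents the number treated at that point in the study". On timing, "An event is defined as progression within 16 weeks" and "The stopping rule assumes monitoring begins after 6 patients have been enrolled on study". The section has no rule for patients whose 16 weeks are not over, and no pause in accrual while outcomes are awaited.

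The operating characteristics table gives a suspension probability of 0.943 and a median of 7 patients at a true rate of 40%. The text repeats this as needing only 7 patients on average.

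Section 12.1 says: "The clinical tumor response will be assessed at baseline and before surgery using RECIST 1.1". The Schedule of Events (Table 1) marks RECIST, mammogram, ultrasound and MRI at baseline and EOT only. Section 9.3 places the last visit "at end of treatment (7 to 10 days after the final dose of study treatment". Table 1 also schedules clinical breast exams at weeks 4, 8, 12 and 16 and a physical exam at every visit, and its footnote n foresees a biopsy on progression during treatment.

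**The concern.** A ratio of events to patients treated is a fair estimate of the event rate only if each treated patient's outcome is already known. Here a patient who started last week adds one to the denominator and cannot yet have contributed an imaging-based event. The faster the accrual, the more such patients there are and the further the ratio is pulled below the true rate.

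This is the only trial-level rule in the documents that can suspend accrual; the other safeguards act on individual patients. The patients are newly diagnosed, have no metastases and are awaiting surgery. A committee relying on the published table would expect a high progression rate to show after about 7 patients, when the rule as written could take considerably longer.

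**Working it through.** **Step 1. Reproduce the plan's figures.** The bound at n patients is the smallest x with P(Beta(0.2 + x, 0.8 + n − x) > 0.20) > 0.85. For example, at n = 12, x = 4 gives 0.829 and x = 5 gives 0.943, so the bound is 5/12. All six bounds reproduce. An exact binomial recursion, checking after every patient from 6 to a maximum of 28 with each outcome known at once, gives:

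| True rate | Published | Recomputed, no delay |
|---|---|---|
| 0.10 | 0.042 | 0.041 |
| 0.20 | 0.317 | 0.316 |
| 0.30 | 0.723 | 0.724 |
| 0.40 | 0.943 | 0.944 (median 7) |
| 0.50 | 0.995 | 0.995 |

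The published table therefore assumes no delay.

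**Step 2. Date the outcome.** The last TAK-228 dose is week 16 day 1, study day 15 × 7 + 1 = 106. The last tamoxifen dose is week 16 day 7, day 112. EOT is 7 to 10 days after the final dose, so it falls on day 113–116 or day 119–122 depending on which drug is meant. Both are after day 112.

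**Step 3. Count the pending patients.** With a lag of about 120 days (120 / 30.4 ≈ 3.9 months), about 4, 8 and 12 patients are pending at 1, 2 and 3 patients per month.

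Take 24 treated patients, of whom 12 have been evaluated with 5 progressions, and no progression yet seen in the other 12. On evaluated patients this is 5/12, a stated bound (posterior 0.943). As written it is 5/24, with posterior P(Beta(5.2, 19.8) > 0.20) = 0.50, and the bound there is 8/24. Accrual continues.

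**Step 4. Simulate the rule as written.** The true rate is 40%, the maximum is 28, accrual is Poisson, and the rule is checked before each enrolment from patient 7. Accrual rates are assumptions, because the documents give none. Entries are the probability of suspension, with median patients enrolled in brackets.

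| Patients/month | Denominator treated; known only at EOT (day 120) | Denominator treated; progression found at week 4/8/12/16 exams | Denominator completed outcomes; known at EOT |
|---|---|---|---|
| No delay | 0.94 (7) | 0.94 (7) | 0.94 (7) |
| 1 | 0.83 (15) | 0.90 (11) | 0.90 (12) |
| 2 | 0.60 (25) | 0.80 (17) | 0.86 (17) |
| 3 | 0.31 (28) | 0.66 (22) | 0.78 (21) |

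At a true rate of 30% with EOT-only knowledge, 0.72 falls to about 0.51, 0.28 and 0.11. Allowing 35 patients instead of 28 softens the EOT-only column to about 0.91, 0.76 and 0.50 (evenly spaced accrual).

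**Step 5. Find where the loss is small.** At 0.5 patients per month, EOT-only knowledge gives about 0.90 (median 11). With events surfacing evenly over the 16 weeks it is about 0.93 (median 8). If the event were a toxicity surfacing evenly over 60 days (an assumption), the rule as written gives 0.93, 0.90 and 0.88 (medians 9, 11, 13) at 1, 2 and 3 per month.

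**The case against.** Four points on the other side have force.

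- **The event itself is unsettled.** Section 13.1 places the prior on toxicity, labels the table by toxicity and sends the safety profile to the committee; one sentence defines the event as progression. If an early toxicity was meant, most of the loss disappears (Step 5). This stands: the size of the problem cannot be separated from that contradiction.
- **EOT-only detection is an extreme.** Besides the scheduled exams and the biopsy on progression, Section 11.12 lists progressive disease as a reason for withdrawal and asks for end-of-study procedures at that time. On-treatment progressions would be counted earlier. This stands, and the middle column of Step 4 reflects it. It reduces the loss without removing it.
- **The accrual rate is assumed.** Slow accrual nearly restores the stated performance. But 35 patients at 0.5 per month take 70 months, and at 0.25 per month 140 months.
- **A crossed bound only suspends accrual for review.** It does not end the trial or touch the Ki67 analysis. This is correct and limits the consequence.

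A reader might infer that the rule would not fire at all, or that most or all patients would be treated first. The documents do not support that as a general statement. It needs detection at EOT only together with faster accrual: the suspension probability at a 40% rate is about 0.06 to 0.12 at 4 per month and 0.00 at 6 per month. Nor is every recent patient necessarily event-free in the count, since progression can be found on treatment.

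**Conclusion.** The fault is real. With the event as defined, a denominator of treated patients and no rule for pending ones, the trial does not have the operating characteristics it publishes; those belong to a rule with immediate outcomes. At a true 40% rate and an assumed 1 to 3 patients per month, the suspension probability is about 0.83 to 0.31 if progression is known only at EOT and about 0.90 to 0.66 if it is found at the scheduled exams, against the stated 0.943. Median enrolment at suspension or end of accrual is 15 to 28 or 11 to 22, against 7. These figures rest on the assumed accrual range, a maximum of 28 (the value that reproduces the table) and the two detection patterns. The loss is small at about 0.5 per month or slower, or for an early toxicity.

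**What to change.** First reconcile in Section 13.1 whether the monitored event is toxicity or progression; the documents leave this open. If it is the 16-week event:

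- Define the denominator as patients whose 16-week/EOT outcome is complete, and start monitoring when there are 6 such patients.
- State how pending patients, on-treatment progressions and progressions first seen at EOT are counted. The last group is found after day 112, so the plan must say whether it falls within 16 weeks. Weighting pending patients by follow-up time is one way to avoid the upward bias of counting early events while leaving out pending non-events.
- State which drug's final dose defines EOT. Reconcile this with the text under Table 7, which puts the EOT visit of discontinued patients 30 to 40 days after the last TAK-228 dose.
- Recompute the table at the planned accrual rate and assessment delay, and replace the statement that only 7 patients are needed with the number expected to be enrolled at suspension.

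The cost is a change of wording and one simulation, with no new procedures. The stated performance will look less favourable. Completed outcomes alone give 0.90 to 0.78 with medians of 12 to 21; 0.944 and a median of 7 return only if accrual is also held until treated patients are evaluated. If events count as they occur while pending non-events are left out, suspension at a true 20% rate becomes about 0.3 to 0.5 against 0.32, each leading to a committee review.

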**FIGURE 1 STUDY OVERVIEW DIAGRAM**

**TABLE 1 SCHEDULE OF EVENTS**

Visit	Screening a	Baseline b	V1	V2	V3	V4	V5	V6	V7*	EOT
Week	-4 to -3	-2 to -1	1	3	4	6	8	12	16*	
Informed Consent	X									
Inclusion/Exclusion	X									
Demographics	X									
Medical History	X									
Physical Exam c		X	X	X	X	X	X	X	X	X
Height	X									
Weight	X	X	X	X	X	X	X	X	X	X
ECOG PS	X	X	X	X	X	X	X	X	X	X
Vital Signs d	X	X	X	X	X	X	X	X	X	X
12-Lead ECG e		X								X
Hematology f		X	X	X	X	X	X	X	X	X
Clinical Chemistry g		X	X	X	X	X	X	X	X	X
FSH/LH/Estradiol h		X								
Serum Pregnancy ( $\beta$ -hCG) i		X								
Urinalysis j		X	X	X	X	X	X	X	X	X
Fasting Lipid Panel k		X			X		X	X	X	X
Bilateral Mammogram and US l		X								X
Breast MRI m		X								X
Clinical Breast Exam		X			X		X	X	X	X
Concomitant Therapies										Continuous from screening period
Tumor Assessments (RECIST 1:1)		X								X
Biopsy n		X					X			
Tumor Tissue o		X				X				
TAK-228 Administration p										Weekly from day 1, week 1 through day 1, week 16
Tamoxifen Administration p										Continuous daily from day 1, week 1 through day 7, week 16
AEs and SAEs										From ICF signing up to and including 30 days after local treatment q
Pharmacokinetics r										Days 1 and 15

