- i. For women of childbearing potential, the results of a serum  $\beta$ -hCG pregnancy test must be negative within 7 days before the first treatment dose is administered. If the screening serum  $\beta$ -hCG pregnancy test is performed more than 7 days before dosing, it must be repeated at baseline, with results known to be negative prior to administration of the first dose of the study drugs.  $\beta$ -hCG pregnancy testing is to be repeated as clinically indicated.
- j. Urinalysis will be performed at baseline, every V, and EOT.
- k. A fasting lipid panel will be obtained at baseline; week 4, 8, 12, and 16 of treatment; and EOT. This panel includes total cholesterol, HDL-C, LDL-C, and triglycerides.
- l. Bilateral mammogram and US will be performed at baseline and EOT. **NOTE:** Bilateral mammogram and US performed as SOC can be used for screening/baseline if performed within 90 days prior to the week 1, day 1 dose of TAK-228 plus tamoxifen.
- m. Breast MRI will be performed at baseline and EOT. **NOTE:** Breast MRI performed as SOC can be used for screening/baseline if performed within 60 days prior to the week 1, day 1 dose of TAK-228 plus tamoxifen.
- n. In patients with accessible tumor, biopsies will be conducted at baseline and week 6 of treatment, and if the patient progresses while on treatment, before the patient starts the new treatment.
- o. Banked tumor tissue obtained as part of the patient's standard care and additional biopsies will be evaluated at a later time to determine the correlation of specific molecular markers (ER; Ki67; mitotic index; apoptosis; levels of S6K, 4EBP-1, EIF4E, EIF4G, and EIF4A; levels of phosphorylated S6K, p53, p63, and p73; and p73 and p63 gene signatures) with clinical parameters such as tumor response. These correlative studies will help define a biomarker signature associated with p63/p73 and/or PI3K/AKT dependence and NFkB in ER-positive breast cancers as well as identify new therapeutic options for this group of patients. Tumor mutational analysis will also be performed to identify predictors of treatment response. Oncotype DX testing will also be performed on biopsy and surgical tissue samples.
- p. TAK-228 30 mg p.o. QW for 16 weeks plus tamoxifen 20 mg p.o. QD for 16 weeks. Adjust dose accordingly with Dose Level (see TAK-228 dose modifications).

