### 13.1.8 Safety Analysis

All patients who received at least 1 dose of the study drugs will be included in a descriptive safety analysis. The safety profiles will be assessed through summaries of AEs, SAEs, AEs leading to treatment discontinuation, and treatment-related death. The safety analysis will report the frequency of all AEs and laboratory abnormalities, as well as the frequency of dose interruptions, dose reductions, and treatment discontinuation for toxicity. Toxicity rates will be presented using the worst NCI CTCAE version 4.03 grade per patient.

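### The accrual-suspension rule in Section 13.1 is introduced as toxicity monitoring but counts progression within 16 weeks, so as defined no toxicity enters it

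*Combined protocol and SAP*

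**What the plan says.** Section 13.1 opens the rule with "As a measure of safety, toxicity will be monitored during the trial based on a beta-binomial model". The prior is placed on the probability of toxicity, a crossing sends the combination's safety profile to the safety monitoring committee, and the operating-characteristics table labels its true rates as toxicity probabilities. Bounds are given as events over patients, where "the denominator represents the number treated at that point in the study".

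The same paragraph then states: "An event is defined as progression within 16 weeks". The two sentences that follow interpret the table as progression rates, for example: "The study has a 94.3% chance of stopping if the true progression rate is 40% and on average would take only 7 patients".

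Elsewhere, safety is summarised without a threshold: "All patients who received at least 1 dose of the study drugs will be included in a descriptive safety analysis" (Section 13.1.8; Section 13.1.3 says the same).

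**The concern.** A committee cannot compute the numerator of 3/6 or 4/8 without first choosing between two different events. Taken literally, a run of severe toxicities triggers no prespecified suspension, while a run of early progressions triggers a review of the safety profile. If the committee instead assumes that toxicity was meant, it has no grade, attribution or time window to apply and would have to invent them during the trial, possibly after seeing data.

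This matters for this pairing because Section 4.2 takes the expected risks of the combination from tamoxifen with everolimus. The toxicity rate of TAK-228 with tamoxifen is what a study-level safety rule would be there to watch.

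The choice of event also affects the printed table. A 16-week event becomes known later than an early toxicity, while the denominator counts everyone treated.

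**Working it through.** **1. The text, side by side (all Section 13.1).**

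| Element | Event implied |
|---|---|
| Stated purpose | toxicity |
| Parameter given the prior | toxicity |
| Action on crossing | review of the safety profile |
| Table column of true rates | toxicity |
| Definition of the counted event | progression within 16 weeks |
| Two sentences interpreting the table | progression |

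The word progression occurs in the definition and in both sentences that interpret the table, so this is not a single slip.

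**2. Is there another study-level toxicity boundary?** Sections 13.1.3 and 13.1.8 are descriptive. The Section 11 holds and discontinuations act on individual patients. Section 11.12 lists "Study termination" among the reasons for which a patient may be withdrawn, with no threshold. Section 14 covers SAE reporting. None was found.

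**3. Reproducing the bounds.** With x events in n patients the posterior is Beta(0.2 + x, 0.8 + n − x), and the bound is the smallest x with Pr(p > 0.20 | data) > 0.85.

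| Bound x/n | Posterior at x | Posterior at x − 1 |
|---|---|---|
| 3/6 | 0.928 | 0.721 |
| 4/8 | 0.959 | 0.838 |
| 5/12 | 0.943 | 0.829 |
| 6/16 | 0.934 | 0.829 |
| 7/20 | 0.928 | 0.831 |
| 8/24 | 0.925 | 0.835 |

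All six match the plan.

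**4. Reproducing the stopping probabilities.** This is an exact recursion over binomial paths, with a check after every patient from 6 to a maximum of 28 and each outcome known at once.

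| True rate | Stated | Recomputed |
|---|---|---|
| 0.10 | 0.042 | 0.041 |
| 0.20 | 0.317 | 0.316 |
| 0.30 | 0.723 | 0.724 |
| 0.40 | 0.943 | 0.944 |
| 0.50 | 0.995 | 0.995 |

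Checking only at the six listed sample sizes gives 0.021, 0.193, 0.561, 0.866 and 0.979, which does not match. These numbers depend on the prior, threshold, looks and maximum, not on what is counted. The defect therefore lies in the event definition.

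**5. Conditional check: delayed outcomes at a true 40% rate** (stated: 0.943, median 7). The plan gives no accrual rate, so a range is assumed. Accrual is Poisson, with 20,000 replicates per cell, the denominator is the number treated, and a stop counts if it comes before patient 28 enters. Cells show probability of stopping (median treated).

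| When the event is known (assumed) | 0.25/month | 0.5 | 1 | 2 | 4 |
|---|---|---|---|---|---|
| (a) Toxicity, uniform over weeks 0–4 | 0.94 (7) | 0.94 (7) | 0.94 (7) | 0.93 (9) | 0.90 (11) |
| (b) Progression, uniform over weeks 0–16 | 0.94 (7) | 0.93 (9) | 0.90 (11) | 0.84 (15) | 0.64 (23) |
| (c) As (b), recognised at next breast exam | 0.94 (7) | 0.92 (9) | 0.89 (11) | 0.80 (17) | 0.49 (28) |
| (d) Recognised only at week 16 | 0.93 (9) | 0.91 (11) | 0.85 (14) | 0.64 (23) | 0.15 (28) |

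At a true 30% rate (stated 0.723), (a) runs from 0.72 to 0.63 and (b) from 0.71 to 0.30 across the same accrual range.

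Row (c) uses the "Clinical Breast Exam" row of Table 1 (weeks 4, 8, 12 and 16). Row (d) is an extreme. Section 12.1 places formal response assessment at baseline and before surgery, but note n of Table 1 provides a biopsy "if the patient progresses while on treatment, before the patient starts the new treatment", so recognition during treatment is expected.

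**The case against.** The strongest reply is that the paragraph as a whole points to toxicity and the event sentence should not override the rest. On that view the text is indeterminate, and it goes too far to say that no toxicity counts. This is fair as a description of intent: the zero contribution holds under the one event definition given. It does not rescue the rule, because reading it as toxicity leaves the event with no grade, attribution or window.

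Progression before surgery might also have been meant as a patient-protection event in its own right. The document does not say so, and the point does not depend on ruling it out.

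The delay figures rest on assumed accrual and timing. That stands. They are secondary: at 0.25 patients per month every scenario stays at 0.93 or above, and an early toxicity event stays close to the stated table throughout. The large losses need both progression as the event and fast accrual.

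Patient-level dose holds, discontinuations and SAE reporting remain in force, so the gap is confined to this study-level rule.

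**Conclusion.** The concern holds and must be fixed. Section 13.1 names two incompatible events for one suspension rule, and under its only event definition toxicities contribute nothing. This conclusion rests on the text alone and needs no numerical assumption. The bounds and stopping probabilities are correct for a binary event known at once.

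Whether the printed table describes the trial depends on the event chosen. For a toxicity arising in the first 4 weeks, stopping at a true 40% rate is 0.90 to 0.94, close to the stated 0.943. For 16-week progression the table is optimistic, by an amount set by the unstated accrual rate and by when progression is recognised.

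**What to change.** Reconcile Section 13.1 so that one event is named throughout.

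- **If it is the safety rule:** replace the event sentence with a toxicity event whose grade, attribution and window the clinical team defines, and change the three references to progression in the interpretation of the table.
- **If early progression is also to be monitored:** write a separate rule with its own bounds and table.
- **Patients still in their window:** count every observed event at once and state how pending patients enter the denominator. One option weights each by the share of the window completed, with a window that matches when events occur.
- **Table:** restate it for the chosen event, window and planned accrual. The present table reproduces with a maximum of 28 patients, while Section 9.2 plans 35, so the maximum should be stated too.

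Simulated at 0.5, 1, 2 and 4 patients per month (6,000 to 10,000 replicates):

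| Time-weighted counting | Stopping at 40% | False suspension at 10% |
|---|---|---|
| 4-week toxicity window | 0.94, 0.94, 0.94, 0.93 | 0.05, 0.05, 0.05, 0.06 |
| 16-week progression, uniform recognition | 0.94, 0.93, 0.92, 0.87 | 0.06, 0.06, 0.07, 0.05 |

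Two choices need care. A 16-week window applied to toxicities that occur in weeks 0–4 raises false suspension at 10% to between 0.07 and 0.20. Leaving pending patients out altogether, for 16-week progression, raises it to 0.10, 0.20, 0.40 and 0.59.

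The cost is a text amendment and a short simulation, with no extra patients or procedures. With a matched window, false suspension at a true 10% rate is about 0.05 to 0.07 against 0.042 stated (0.03 to 0.07 if progression is recognised at breast exams), and the restated stopping probabilities may be slightly less favourable.

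### The accrual rule has no provision before the 6th patient; suspending at a third early event would cost nothing statistically and could spare up to 3 patients (optional refinement)

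*Combined protocol and SAP*

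**What the plan says.** Section 13.1 (Statistical Methods) gives the event probability a beta(0.2, 0.8) prior and acts when the posterior probability of a rate above 0.20 exceeds 0.85. The action is that "Study accrual will be suspended and the safety profile of the TAK-228 and tamoxifen combination will be reviewed by the safety monitoring committee".

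The bounds are listed as "3/6, 4/8, 5/12, 6/16, 7/20, 8/24". In each pair "the numerator represents the number of events needed to suspend accrual" and "the denominator represents the number treated at that point in the study". On the start of monitoring the section says: "The stopping rule assumes monitoring begins after 6 patients have been enrolled on study". On what is counted: "An event is defined as progression within 16 weeks".

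No bound is listed below 6 patients and nothing is said about three events before the 6th. The operating characteristics table agrees with this: no median or quartile in its patient-count column is below 6.

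**The concern.** Event counts cannot fall. If the third event is recorded when only 3, 4 or 5 patients have been treated, the count at patient 6 will be 3 or more whatever happens next, and the suspension is already determined. Read literally, the rule would still let accrual run on to the 6th patient. Between one and three further patients could then start a combination under review for safety, without any influence on whether the review takes place. The cases in which this happens are mostly those in which the regimen performs badly, which are the cases the rule exists to catch.

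**Working it through.** **Inputs (all from section 13.1).** Prior beta(0.2, 0.8); reference rate 0.20; threshold 0.85; monitoring from patient 6; maximum of 28 patients, taken from the operating characteristics table.

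**Step 1: reproduce the plan.** With x events in n patients the posterior is beta(0.2 + x, 0.8 + n − x), and the criterion is 1 − F(0.20; 0.2 + x, 0.8 + n − x) > 0.85, where F is the beta distribution function. At n = 6, 2 events give 0.721 and 3 give 0.928, so the bound is 3/6. The other five listed bounds reproduce in the same way.

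An exact forward recursion, checking after every patient from 6 to 28, gives:

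| True rate | Pr(stop early), plan | Pr(stop early), recomputed |
|---|---|---|
| 10% | 0.042 | 0.041 |
| 20% | 0.317 | 0.316 |
| 30% | 0.723 | 0.724 |
| 40% | 0.943 | 0.944 |
| 50% | 0.995 | 0.995 |

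The medians and quartiles of the patient count also agree, apart from the lower quartile at 20% (17 recomputed, 15 stated) and the median at 30% (13 recomputed, 14 stated).

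**Step 2: is the decision fixed early?** The posterior is 0.996 at 3/3, 0.983 at 3/4 and 0.960 at 3/5. All exceed 0.85, and each state leads with certainty to at least 3/6. Two early events are different. The posterior is 0.979 at 2/2, 0.932 at 2/3 and 0.869 at 2/4, but it falls back to 0.797 at 2/5 if no further event occurs. Only the third event settles the matter.

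**Step 3: how often.** The chance of three or more events in the first five patients is Σ C(5, k) p^k (1 − p)^(5−k) over k = 3, 4, 5. The third event falls at patient n with probability C(n−1, 2) p³ (1 − p)^(n−3), and suspending there spares 6 − n patients. At p = 0.40 the probabilities for patients 3, 4 and 5 are 0.0640, 0.1152 and 0.1382. They sum to 0.317, and the mean saving is 3 × 0.0640 + 2 × 0.1152 + 1 × 0.1382 = 0.56.

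| True rate | Third event by patient 5 | Mean patients, as written | Mean patients, with early suspension | Mean saving (upper limit) |
|---|---|---|---|---|
| 10% | 0.9% | 27.23 | 27.22 | 0.01 |
| 20% | 5.8% | 22.75 | 22.66 | 0.09 |
| 30% | 16.3% | 15.81 | 15.53 | 0.27 |
| 40% | 31.7% | 10.45 | 9.89 | 0.56 |
| 50% | 50.0% | 7.72 | 6.78 | 0.94 |

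The recursion with early suspension gives the same probability of stopping early in all five scenarios, as it must: every path stopped early would have stopped at patient 6 anyway.

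**Step 4: sensitivity to timing.** These savings assume each event is known before the next patient enters. The documents give no accrual rate, so take even entry gaps of g weeks and a fixed lag of L weeks from entry to a known event (both assumptions). Patient 3's outcome is known at 2g + L and patient 6 enters at 5g, so nobody is spared if 3g < L. The full saving needs g ≥ L.

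- L = 16: nobody is spared if g is under 16/3 = 5.3 weeks, which means 35 patients entered within about 34 × 5.3 ≈ 181 weeks (3.5 years). The full saving needs 34 × 16 = 544 weeks (10.4 years).
- L = 8: the full saving needs 34 × 8 = 272 weeks (5.2 years).

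**The case against.** The run-in is a disclosed choice and has a purpose. The prior carries the weight of one patient, so one event in the first patient gives 0.884 and would suspend accrual. Monitoring from patient 1 would raise the probability of stopping at a true rate of 10% from 0.041 to 0.142. This stands, and it is why the run-in should stay. It is no argument against acting on a third event, which leaves these probabilities untouched.

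The practical saving may be small or nil. The event is progression within 16 weeks, section 12.1 places RECIST assessment at baseline and before surgery only, and accrual speed is not stated. Clinical breast examination at weeks 4, 8 and 12 (Table 1) could reveal some progression sooner. This stands too: the savings are ceilings.

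A reader might infer three stronger things that the documents do not support:

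- **That the protocol requires accrual to continue after three early events.** The text says only what the rule assumes about the start of monitoring. The posterior criterion is stated without a minimum number of patients, and nothing forbids an earlier review. The gap is that none is provided for.
- **That the extra patients are exposed for nothing.** They cannot change the suspension, but meeting the bound leads to suspension and review, not termination. Their safety, Ki67 and pharmacokinetic data still count.
- **That the median patient count at a 50% rate would fall from 6 to 5.** The chance of three events by patient 5 is exactly 0.50 there, so the median is a tie between 5 and 6.

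**Conclusion.** The point holds as an optional refinement. The stopping rule is correctly derived and its stopping probabilities reproduce to within 0.001. What it lacks is a provision for the three early states (3/3, 3/4, 3/5) in which suspension is already certain. Adding one changes no probability of stopping early. It saves at most 3 patients in a single trial, and on average at most 0.01 to 0.94 across the five scenarios, with almost all of the benefit at high event rates. Those averages rest on independent events at a constant rate, each known before the next entry. The actual saving lies between zero and these figures, depending on accrual speed and on how soon progression is detected.

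**What to change.** Keep the run-in and the listed bounds, and add to section 13.1: *If three events are recorded before 6 patients have been treated, accrual is suspended and the committee review starts at that point; from the 6th treated patient the listed bounds apply.* The wording counts treated patients, as the bounds do. The run-in sentence counts enrolled patients, and section 9.2 dates enrolment from consent.

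Then refresh the patient-count column of the operating characteristics table. For example, the lower quartile at a 40% rate moves from 6 to 5, since the probability of stopping is 0.179 by patient 4 and 0.317 by patient 5. The stopping probabilities, bounds, sample size and study procedures stay as they are. The cost is one sentence and one recalculated column.
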